8.2.2 Specific ocular tests

Specific complete ocular tests will include: assessment of ocular/visual symptoms and ocular exams.

Ocular/visual symptoms must be assessed by the Investigator at screening, at each visit before study treatment administration (including C1D1), at EOT, and whenever clinically indicated. If any visual symptom is reported, an ophthalmologist visit must be scheduled.

Specific ocular tests performed by the ophthalmologist at screening, at EOT, and whenever indicated will include:

- Visual acuity.
- Slit lamp under dilatation.
- Schirmer's test.

In participants with any ocular/visual symptom (eg, blurred vision, photophobia), complete ocular tests will be repeated at the time of the occurrence of the ocular toxicity, if any, regardless of the grade. Thereafter, visual acuity, slit lamp examination under dilatation, and Schirmer's test will be repeated once weekly (if not recommended to have less frequent assessment by ophthalmologist based on lesion characteristics) until resolution to Grade 1. In case of recurrent ocular toxicity observed in subsequent cycles, visual acuity and slit lamp examination under dilatation, and Schirmer's test will be performed at the time of the event onset, then weekly until resolution to Grade 1. Schirmer's test is mandatory for baseline assessment; it can be omitted from further ocular assessments if not considered a required examination per reported events category (ie, no symptom/findings of dry eye).

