3.6.3.2 Ocular examinations

Schirmer test

Participants reported Schirmer's test will be classified into three classes at baseline: normal ≥ 10 mm, moderate >5 and <10 mm, severe ≤ 5 mm (8). The worst classification between the laterality will be considered. A frequency table of the baseline status with and without anaesthetics will be provided by treatment group for the participants with corneal events (CMQ) during the treatment-emergent period and for the participants without event.

Visual acuity test

Analyses are done on the best corrected visual acuity assessed using Snellen Chart method.

Frequency tables on best corrected visual acuity (BCVA) measured during on-treatment period will be performed separately on all participants and on participants who experienced at least one treatment-emergent corneal event:

- on the worst change from baseline: No worsening versus baseline, Worsening versus baseline (1 to 3 lines decrease versus baseline, or >3 lines decrease versus baseline)
- on the worst absolute value: No change versus baseline, Worsening versus baseline: BCVA equals to 20/40 or better, BCVA worse than 20/40 up to 20/200, BCVA 20/200 or worse.

- on the CTCAE worst vision decrease: No worsening versus baseline, BCVA equals to 20/40 or better or 1 to 3 lines decrease versus baseline, BCVA worse than 20/40 up to 20/200 or >3 lines decrease versus baseline, BCVA 20/200 or worse.
- For participants who had worsening versus baseline on BCVA, the outcome on the last BCVA value will be displayed: Recovered to baseline, Not recovered to baseline, Lost to follow-up or dead with ongoing corneal events

A participant will be considered as lost to follow-up if the participant discontinued the study and did not perform any follow-up visit.

A shift table of the category of the last BCVA value (Normal (20/20 or better), worse than 20/20 up to 20/40, worse than 20/40 up to 20/200 or 20/200 or worse) versus the category of the worst BCVA value (20/40 or better, worse than 20/40 up to 20/200, 20/200 or worse) will be performed for participants who experienced at least one treatment-emergent corneal event.

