For the summary table on participants who experienced at least one treatment-emergent corneal event, the worst value and the worst change from baseline are measured during any of the treatment-emergent corneal events experienced by the participant (between start date and end date of the corneal events). For the summary table on all participants, all on-treatment BCVA values are considered.

The worst classification between the laterality will be considered for the worst value of participant either left or right eye then the change from baseline and the last value will be measured from same eye with worst value. If the worst absolute value is the same for both eyes, then the eye with the worst change from baseline is considered, and if identical, then the eye with the worst last value is considered.

Participants whose baseline visual acuity had been reported in naked eye instead of BCVA (ie, whenever baseline value was worse than the values reported during the during the treatment period/treatment-emergent corneal events) will be excluded from this analysis.

Slit lamp examination

Descriptive statistics of slit lamp examination will be provided separately at baseline and at the time of first abnormal slit lamp after occurrence of a treatment-emergent corneal event and at the time of the worst BCVA value during a treatment-emergent corneal event for participants experiencing treatment-emergent corneal events (CMQ). The outcome (normal, abnormal), and for abnormal findings, the type of lesions and the distribution will be described by laterality (unilateral, bilateral, all).

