4 SAMPLE SIZE DETERMINATION

Assuming a pre-screening failure rate of 84% and a study screening failure rate of 15%, approximately 285 participants will be pre-screened to achieve approximately 38 treated participants in the study.

The initial plan is to treat a total of 38 participants evaluable for anti-tumor activity (at least 1 postbaseline tumor assessment, early clinical progression, or death due to disease progression).

Estimated ORR and 95% exact CIs by number of responders from a sample size of 38 evaluable participants for anti-tumor activity are listed in Table 7.

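### The SAP identifies naked-eye baseline acuity from the on-treatment result, so the BCVA exclusion depends on the outcome and can push the reported worsening percentage upward

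*SAP*

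**What the plan says.** SAP 3.6.3.2 (Visual acuity test) sets the measure: "Analyses are done on the best corrected visual acuity assessed using Snellen Chart method". Participants are then tabulated "on the worst change from baseline: No worsening versus baseline, Worsening versus baseline", with further tables by worst absolute value and by CTCAE-type vision decrease. The tables are produced for all participants and again for those with a treatment-emergent corneal event. "For the summary table on all participants, all on-treatment BCVA values are considered", while the corneal-event table uses values between the start and end dates of the events.

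The exclusion comes at the end of the visual acuity text. It covers "Participants whose baseline visual acuity had been reported in naked eye instead of BCVA (ie, whenever baseline value was worse than the values reported" on treatment or in a corneal event, and these participants "will be excluded from this analysis". The wording makes the comparison with later values the definition of a naked-eye baseline, not an example of one or a prompt to check.

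Neither document gives another way to recognise such a baseline. Protocol 8.2.2 lists visual acuity among the ophthalmologist's tests without stating that it must be best corrected. The SAP plans no count or listing of the excluded participants, and no version of the tables that keeps them.

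**The concern.** Whether a participant enters the analysis depends on the difference between baseline and later acuity, which is the quantity being tabulated. A baseline worse than later readings may mean that it was taken without correction. It may also mean that vision improved, or that the two readings differ by ordinary test variation. The rule treats all of these alike.

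Chance differences matter here because readings may be few. Protocol 8.2.2 states: "Specific ocular tests performed by the ophthalmologist at screening, at EOT, and whenever indicated will include" visual acuity, slit lamp and Schirmer's test. A participant without ocular symptoms may have a single post-baseline value, and one better reading would then be enough for removal.

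At stake is how far the BCVA tables can be trusted as an objective description of vision change, for a drug whose main anticipated risk is corneal toxicity (Protocol 2.3.1). The rule also leaves open whether all later values or any one of them must be better, and which eye counts. Two programmers could produce different tables.

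**Working it through.** **Inputs**
- N, all-participants table: about 38 treated (SAP 4).
- N, corneal-event table: not stated. The first-in-human study reported corneal events in 56/186 = 30.1% at this dose (Protocol Table 1), and 38 × 0.301 = 11.4, so about 11 is used.
- w (number worsening), k (number excluded), test variation and the share of true naked-eye baselines: not in either document. Every value below is an assumption.

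**Step 1. The plan's own figure.** The plan gives no BCVA worsening rate or exclusion count to reproduce. Only the denominator can be checked. The SAP says "approximately 285 participants will be pre-screened to achieve approximately 38 treated participants in the study", and 285 × (1 − 0.84) × (1 − 0.15) = 38.8, which agrees.

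**Step 2. If all later values must be better than baseline.** The worst later value is then also better than baseline, so each excluded participant is a non-worsener. The percentage moves from w/N to w/(N − k), which is larger whenever w and k are above zero.

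| N | w | All kept | After wrongly removing k non-worseners |
|---|---|---|---|
| 38 | 8 | 8/38 = 21.1% | k = 2: 8/36 = 22.2%; k = 4: 8/34 = 23.5%; k = 8: 8/30 = 26.7% |
| 11 | 5 | 5/11 = 45.5% | k = 1: 5/10 = 50.0%; k = 2: 5/9 = 55.6%; k = 4: 5/7 = 71.4% |

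**Step 3. If any better value, or either eye, is enough.** A participant with one better and one worse reading is a worsener and is still dropped. Suppose x of the k excluded are worseners. The rate becomes (w − x)/(N − k), which exceeds w/N only if x/k is below w/N. The direction is therefore not fixed by algebra.

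In a simulation with no true change, three later readings, and test variation of SD 0.5 Snellen line rounded to whole lines, 43.4% appear to worsen with everyone kept.
- All-values reading: the rate becomes 48.1%.
- Any-value reading: 43.4% of participants are excluded, and worseners who are excluded make up 8.8% of all participants. So x/k = 8.8/43.4 = 20%, below 43.4%, and the rate rises to 61.2%.

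In a two-eye version (SD 0.5, one visit), 28% of those excluded were worseners and the rate still rose. The rate rose in every case simulated.

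**Step 4. Allowing for true naked-eye baselines.** Assume 30% truly lose 1–3 lines, 20% have a naked-eye baseline 2–5 lines worse, and each participant contributes one eye and one later reading.

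| Test variation | Keep everyone | SAP rule | Exclude by record |
|---|---|---|---|
| SD 0.25 line | 26.6% | 33.6% | 32.6% |
| SD 0.5–1.0 line | – | 53–68% | 44–50% |

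With a precise test the rule is about 1 point from exclusion by record, and keeping everyone is about 6 points below it. With a noisier test the rule clearly overstates. If there are no naked-eye baselines at all and SD is 0.25, the shift is only from 32.7% to 33.8%.

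**Step 5. Does the rule find what it seeks?** Not always. If the baseline was uncorrected and later corrected acuity has fallen to that level or below, baseline is not worse than the later values. The participant stays in, and the loss is understated.

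**Step 6. Band edges.** The SAP lists "BCVA worse than 20/40 up to 20/200, BCVA 20/200 or worse". Exactly 20/200 satisfies both.

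**The case against.** The strongest defence is that the rule corrects a real bias in the other direction. The analysis is defined on best-corrected acuity, and keeping uncorrected baselines understates vision loss. Step 4 shows that with a precise test and a fair number of such baselines the rule does better than keeping everyone. That stands, and it is why the remedy is a better identifier and not removal of the exclusion.

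A reader might also infer more than the documents support:
- *That the main ocular safety result is inflated.* BCVA falls under the additional safety assessments (SAP 3.6.3). The corneal event overview, the grade tables, Grade ≥3 keratopathy/keratitis as an event of special interest, and the onset, recovery and recurrence analyses are in SAP 3.6.2 and do not use this exclusion.
- *That everyone excluded is a non-worsener.* This holds only under the all-values reading. The SAP does not specify all or any value, or which eye triggers the rule.
- *That a definite inflation can be stated.* The earlier 30.1% is a corneal event rate, not a vision-worsening rate, and neither document gives an exclusion count or a figure for test variation.
- *That one participant would be counted in both of the worst bands.* The SAP selects one worst eye and value per participant, so double counting is unlikely. The defect is an undefined edge. Protocol Table 10 has the same overlap between its Grade 3 and Grade 4 keratopathy descriptions.

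**Conclusion.** As written, the rule conditions the BCVA analysis set on the outcome. It removes participants who improved or varied by chance, and it can retain a naked-eye baseline that later loss has masked. Under the all-values reading the worsening percentage among those remaining can only be pushed upward. Under the any-value or either-eye reading an upward shift is likely but not assured.

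The size is not derivable from the documents. It depends on the unknown share of naked-eye baselines and on test variation, so the 38-participant example (21.1% moving to between 22.2% and 26.7%) shows scale only. It also assumes that percentages use the participants left after exclusion, as the wording implies. If the denominator stayed at all treated, the all-values reading would leave both the count and the percentage of worseners unchanged.

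The effect is confined to descriptive BCVA tables. Corneal event analyses, ORR and the interim rule are untouched. The 20/200 overlap is a minor edit.

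**What to change.** In SAP 3.6.3.2:
1. Exclude a participant only where the record shows that baseline acuity was taken without correction.
2. Use a baseline worse than later values only to trigger a data query on correction status. State whether all or any later values, and which eye, trigger it.
3. Keep all other participants in their observed category, including no worsening.
4. Report and list the number excluded, and show the BCVA tables with and without the exclusions.
5. Make the table bands exclusive so that exactly 20/200 falls in one category, and reconcile this with the keratopathy grading in Protocol Table 10.

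The cost is SAP wording, a few data queries where correction status was not captured, and one extra set of BCVA tables.

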3.6.3.3 ECOG PS

A shift table of baseline ECOG PS versus last and worst ECOG PS on treatment will be provided.

3.7 OTHER ANALYSES

3.7.1 Other variables and/or parameters

3.7.1.1 PK analyses

All concentration values below the LLOQ will be treated as zero in individual listings and respective descriptive statistics. The geometric mean will not be computed in case at least one concentration is below LLOQ.

Individual observed predose concentrations (C_{trough}) and concentrations observed at end of infusion (C_{eoi} , C_{eoi} +1h if any) of tusamitamab ravtansine will be listed and summarized with standard descriptive statistics (such as the number of observations, arithmetic and geometric means, median, standard deviation, standard error, coefficient of variation, minimum, and maximum) by visit.

For the descriptive statistics, Ctrough following any dose modification (delay or reduction as defined in Section 3.6.1 will be excluded. Ceoi and Ceoi+1h will be excluded following dose reduction.

A graphical representation of mean Ctrough (\pm SD) profile over time, will be provided throughout the course of treatment.

3.7.1.1.1 Population PK analysis

The population PK analyses will be described in a specific document and the results will be presented separately from the clinical study report.

3.7.1.1.2 IgG

In the all-treated population, the level of IgG in blood at pre-infusion of Cycle 1 Day 1 will be summarized with standard descriptive statistics (such as the number of observations, arithmetic and geometric means, median, standard deviation, coefficient of variation, minimum and maximum). A listing will also be provided.

3.7.1.2 Immunogenicity analyses

Participant's ATA status, response variable, and kinetics of ATA responses (see definitions below) will be summarized on the ATA population.

Kinetics of ATA responses will be described for participants with treatment-induced ATA and for participants with treatment-boosted ATA, separately. Time to ATA onset and duration of ATA will be described with minimum, Q1, median, Q3, and maximum statistics.

Peak titer will be described with minimum, Q1, median, Q3, and maximum statistics for participants with treatment-induced ATA and for participants with treatment-boosted ATA, separately.

Sample status (negative, positive, inconclusive) and titers will also be described overtime using descriptive statistics.

The impact of positive immune response on efficacy, PK, and safety variables may be further explored, depending on ATA incidence.

Participant's ATA status

- Participants with **pre-existing ATAs** correspond to participants with ATAs present in samples drawn before first administration of intervention. Participants with missing ATA sample at baseline will be considered as without pre-existing ATA.
- Participants with **treatment-emergent ATA** correspond to participants with at least 1 treatment-induced/boosted ATA.
 - Participants with **treatment-induced ATAs** correspond to participants with ATAs that developed at any time after IMP administration and without pre-existing ATA (including participants without pre-treatment samples).
 - Participants with **treatment-boosted ATAs** correspond to participants with preexisting ATAs that are boosted at any time after IMP administration to a significant higher titer than the baseline. A 2-fold serial dilution schema is used during titration, so at least a 4-fold increase will be considered as significant.
- Participants with **unclassified ATA** correspond to participants with pre-existing ATAs that cannot be classified as treatment-boosted ATA because of missing titer(s) (ie, a positive ATA sample at any time after IMP administration in a participant with pre-existing ATA but with missing titer at this sample or at baseline).
- Participants without treatment-emergent ATA correspond to participants without treatment-induced/boosted ATA and without any inconclusive sample nor unclassified ATA at any time after IMP administration .
- Participants with inconclusive ATA are defined as participants which cannot irrefutably be classified as with or without treatment-emergent ATA.

Kinetics of ATA response

Kinetics of ATA response will be derived for participants with treatment-induced/boosted ATA.

- **Time to onset of ATA response** is defined as the time period between the first IMP administration and the first treatment-induced/boosted ATA.
- **Duration of ATA response** is defined as the time between the first treatment-induced/ boosted ATA and the last treatment-induced/boosted ATA, irrespective of negative samples or positive samples not reaching the boosted threshold in-between. ATA duration will be summarized only for participants with persistent ATA response.

- **Persistent ATA response** is defined by treatment-induced/boosted ATA with a duration of ATA response of at least 16 weeks.
- **Transient ATA response** is defined by treatment-induced/boosted ATA with a duration of ATA response of less than 16 weeks and the last sample is not treatment-induced/boosted.
- Indeterminate ATA response is defined by treatment-induced/boosted ATA that are neither persistent nor transient.

ATA response variable:

• ATA incidence is defined as the proportion of participants found to have seroconverted (treatment-induced ATAs) or boosted their pre-existing ATA response (treatment-boosted ATAs) at any time point after first IMP administration.

3.7.2 Biomarker analyses

Several exploratory objectives related to pharmacodynamic/genomic endpoints will be considered in this study.

Unless otherwise specified, biomarkers analyses will be performed on participants with available data from the all-treated population.

3.7.2.1 Circulating CEA

The circulating CEA will be considered as a quantitative variable and circulating CEA values below the LLOQ will be replaced by half of the LLOQ.

3.7.2.1.1 Circulating CEA levels before IMP and CEACAM5 IHC

Circulating CEA levels before IMP will be correlated with IHC CEACAM5 expression status (for prescreened participants). To this end, the closest circulating CEA assessment to biopsy (or the oldest value before IMP if the date of the biopsy is missing) will be considered. The circulating CEA levels (quantitative) will be presented using descriptive statistics, according to IHC CEACAM5 expression status (negative vs. moderate expressers; or according to the % of tumoral cells expressing CEACAM5 at intensity $\geq 2+$). The association between the circulating CEA levels (quantitative) and the CEACAM5 expression will be also assessed and visualized graphically. The time from tumor biopsy collection and circulating CEA assessment (the closest to biopsy) will be also described and investigated in the correlation between circulating CEA levels and IHC CEACAM5 expression.

In order to evaluate the variability of circulating CEA values, an intraclass correlation coefficient will be calculated between pre-screening and screening circulating CEA values (when both available). A graphical visualization may be provided to observe the degree of concordance. Similarly, the concordance between the circulating CEA and the circulating CEACAM5 will be evaluated.

3.7.2.1.2 Modulations of circulating CEA as a potential PD biomarker of response to tusamitamab ravtansine treatment

The circulating CEA at different timepoints and its relative change from baseline will be presented using descriptive statistics by response status and overall. Depending on the data available, some timepoints may not be presented when the sample size is too small.

A graphical visualization (spaghetti plot) will be presented to visualize the relative change from baseline of circulating CEA values for each participant, annotated with the best overall response.

